**Table 1 Efficacy analyses per study periods and age-strata**

Analysis	Study period	≥ 50 YOA	≥ 60 YOA	≥ 70 YOA	50-59 YOA	60-69 YOA	70-79 YOA	≥ 80 YOA	Objective
A	Z-049 duration overall	X	X	X	X	X	X	X	Primary and Secondary
B	Z-006/Z022 * + Z049 duration overall	X	X	X	X	X	X	X	Secondary
C	Z-006/022 + Z-049 duration yearly**	X	X	X	X	X	X	X	Secondary and CCI

YOA = Year of age

\* from one month post dose 2 in the ZOSTER-006/022 studies

\*\* yearly follow-up will be computed from one month post dose 2 in the ZOSTER-006/022 studies. Note that results from the pooled ZOSTER-006/022 studies will be presented for each year after vaccination with methods used in these studies.

The primary analysis of efficacy will be performed on the mTVC, the analysis will be also performed on the TVC for efficacy and the ATP for efficacy to complement the mTVC analysis.

The **VE analysis for HZ** on TVC, mTVC and ATP cohort for efficacy over the study duration of present study ZOSTER-049 will be performed over the follow-up time calculated from enrolment in the present study to the time of first confirmed HZ case for a subject with a confirmed HZ case, and to the date of last contact for subjects without the occurrence of confirmed HZ case.

The **VE analysis for HZ** on mTVC and ATP cohort for efficacy over the duration starting from ZOSTER-006/ -022 study will be performed over the follow-up time calculated from one month post Dose 2 to the time of first confirmed HZ case for a subject with a confirmed HZ case, and to the date of last contact for subjects without the occurrence of confirmed HZ case.

The **VE analysis for HZ** on the TVC will be performed over the complete follow-up period and will include confirmed HZ cases from Dose 1 administered in the ZOSTER-006/022 studies for vaccine efficacy evaluation. The end of the follow-up period will be calculated according to the same principle as will be done for the mTVC and ATP analyses for efficacy, i.e., up to the confirmed HZ case for a subject with a confirmed HZ case, or up to the date of last contact for subjects without a confirmed HZ case.

***In the VE analysis for PHN and HZ related complication (other than PHN), the follow-up time will be calculated in the similar way as in VE analysis for HZ.***

All above analyses will be performed overall and by age strata. The age strata for VE are defined as: **50-59, 60-69, 70-79, ≥80, ≥60, ≥70 YOA** at primary vaccination in ZOSTER-006/022 studies.

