#### 6.2.2.3. **Sensitivity analysis considering subjects aging when enrolled into ZOSTER-049 from ZOSTER-006/022**

*Since all subjects enrolled in ZOSTER-049 study had aged for ~5 years compared to when they were enrolled in ZOSTER-006/022 studies, a sensitivity analysis on VE (analysis A, B and C on mTVC - LTFU and Control group only.) is planned to consider the aging factor on ZOSTER-049 subjects when utilizing the historical control to estimate the incident rate on the hypothetical control in ZOSTER-049 study. Please refer to Section 7.3.6 for more details*

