For the clinical endpoint linked to a **confirmation of HZ**, since there is no possibility to confirm a suspected HZ case during the gap, the follow-up time for subjects who came back to ZOSTER-049 will be computed minus the gap between the end of study efficacy cut-off date (21 April 2015) of ZOSTER-006/022 and the first visit for each subject **in ZOSTER-049**.

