***To note - North America is used as reference group***

2. Determine the Age adjusted historical control rate:

Using the coefficients from the Poisson regression in (1), the age-specific HZ incidence rates for an age stratum for Placebo group will be calculated as:

$$\text{Age specific } r_{\text{HZhistorical control reference group}} = \exp(\alpha + \beta_{\text{Australasia}} * \text{Region_Australasia} + \beta_{\text{Europe}} * \text{Region_Europe} + \beta_{\text{Latin America}} * \text{Region_Latin America})$$

Once the age-specific incidence rates are calculated for the historical control data from the ZOSTER-006 and ZOSTER-022, the results will be used to calculate age-specific controls rates on the hypothetical control group for the ZOSTER-049 interim and final analyses.

3. Determine the number of HZ cases for the age adjusted historical controls:

For each scheduled analysis, the age-specific follow-up time observed in ZOSTER-049 will be used as the follow-up time on the corresponding age-specific hypothetical control on ZOSTER-049. The total number of subject-years of HZ surveillance ( $F_{\text{Age}}$ ) for each age-strata will be then multiplied by the age-specific incidence rate that was estimated from step 2, to obtain the expected number of evaluable cases of HZ ( $n_{\text{Age}}$ ) for a specific age strata in the hypothetical control in ZOSTER-049:

$$n_{\text{Age}} = F_{\text{Age}} * \exp(\alpha + \beta_{\text{Australasia}} * \text{RegionAustralasia} + \beta_{\text{Europe}} * \text{RegionEurope} + \beta_{\text{Latin America}} * \text{RegionLatin America})$$

Once the expected number of cases for the hypothetical controls are determined for each age strata, expected HZ incidence rate for the hypothetical controls will be calculated by summing the numbers of expected evaluable cases of HZ for each age strata, and dividing by the total number of subject-years of HZ surveillance among all subjects during the ZOSTER-049 study.

*For the overall calculation of VE starting from the ZOSTER-006/022 study, the observed incidence rate for Placebo during ZOSTER-006/022 and the predicted incidence rate during ZOSTER-049 will be used in the calculation.*

*In the situation that there are very few subjects during the last year of follow-up with limited total follow-up time, data from both year 11 and year 12 will be pooled in the VE analysis.*

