*For the sensitivity analysis considering subjects aging when enrolled into ZOSTER-049 from ZOSTER-006/022. The same step 1,2 and 3 will be used to calculate the incidence rates on ZOSTER-049 historical control using data from ZOSTER-006/022 control. The only difference is that estimated incidence rates will be applied to the age-specific group based on the approximate age in years when the subjects were enrolled in the beginning of study ZOSTER-049 to estimate the HZ cases in the hypothetical control.*

*For the VE analysis for PHN or HZ related complication (other than PHN) the same poison regression models detailed in step 1, 2 and 3 will be used to generate the hypothetical controls for the incidence of PHN or HZ related complication (other than PHN) in study ZOSTER-049.*

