## CONFIDENTIAL

201190 (ZOSTER-049 EXT:006-022)  
Statistical Analysis Plan Amendment 3

ZOSTER-006/022 control		ZOSTER-049 hypothetical control (estimated HZ cases to be used in 049 VE analysis)				
55-59 YOA (at primary vaccination )	IR2	55-59 YOA (at Z-049 enrollment)	N1	FT_1	IR2	$n1=FT1*IR2$
60-64 YOA (at primary vaccination )	IR3	60-64 YOA (at Z-049 enrollment)	N2	FT_2	IR3	$n2=FT2*IR3$
65-69 YOA (at primary vaccination )	IR4	65-69 YOA (at Z-049 enrollment)	N3	FT_3	IR4	$n3=FT3*IR4$
70-74 YOA (at primary vaccination )	IR5	70-74 YOA (at Z-049 enrollment)	N4	FT_4	IR5	$n4=FT4*IR5$
75-79 YOA (at primary vaccination )	IR6	75-79 YOA (at Z-049 enrollment)	N5	FT_5	IR6	$n5=FT5*IR6$
80-84 YOA (at primary vaccination )	IR7	80-84 YOA (at primary vaccination)	N6	FT_6	IR7	$n6=FT6*IR7$
>=85 YOA (at primary vaccination )	IR8	>=85 YOA (at Z-049 Enrollment)	N7	FT_7	IR8	$n7=FT7*IR8$

The resulting HZ cases for age strata defined by subjects' age at first vaccination in ZOSTER-006/022 studies are then calculated in the following way which are to be used in the VE sensitivity analysis by strata following the same methodology used in VE Analysis A, B and C:

HZ cases for 50-59 YOA:  $n1+n2$

HZ cases for 60-69 YOA:  $n3+n4$

HZ cases for 70-79 YOA:  $n5+n6$

HZ cases for >=80 YOA:  $n7$

Since all subjects in ZOSTER-049 study were  $\geq 55$  YOA at their enrollment, for the overall VE sensitivity analysis, subjects who were 50-54 YOA at primary vaccination were excluded from the ZOSTER-006/022 Placebo group when building the

*hypothetical control. The estimated IR are then multiplied by the total follow-up time observed in ZOSTER-049 study to obtain the estimated HZ cases, which will be subsequently used to calculate overall VE following the same methodology used in VE Analysis A, B and C.*

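### In the ageing sensitivity analysis, SAP 7.3.6 gives an overall rule that does not match SAP 7.3.3 and returns control cases to strata by a fixed 5-year shift; the effect is small and the primary VE is untouched

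*SAP*

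**What the plan says.** SAP 6.2.2.3 motivates the analysis by noting that subjects "had aged for ~5 years compared to when they were enrolled in ZOSTER-006/022 studies", and applies it to VE analyses A, B and C.

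**Strata.** The table in SAP 7.3.6 defines expected control cases n1 to n7 for the enrolment-age bands 55-59, 60-64, 65-69, 70-74, 75-79, 80-84 and 85 or older. Each is ZOSTER-049 follow-up in the band times the placebo rate for the same ages at primary vaccination. Cases for strata defined by "age at first vaccination in ZOSTER-006/022 studies are then calculated in the following way which are to be used in the VE sensitivity analysis". The assignment is n1+n2 to 50-59, n3+n4 to 60-69, n5+n6 to 70-79, and n7 to 80 or older.

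**Overall.** SAP 7.3.6 excludes placebo subjects vaccinated at 50-54, then: "The estimated IR are then multiplied by the total follow-up time observed in ZOSTER-049 study to obtain the estimated HZ cases". SAP 7.3.3 says of the same analysis that steps 1 to 3 are kept and "The only difference is that estimated incidence rates will be applied to the age-specific group based on the approximate age in years" at ZOSTER-049 enrolment. Step 3 obtains the overall control rate by "summing the numbers of expected evaluable cases of HZ for each age strata, and dividing by the total number of subject-years".

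**Interval.** SAP 6.3.3 and Protocol 1.2.2 say the time to ZOSTER-049 start varies between subjects. SAP 7.3.1 computes follow-up "minus the gap between the end of study efficacy cut-off date (21 April 2015) of ZOSTER-006/022 and the first visit for each subject". SAP 7.2 derives age at enrolment by adding each subject's own elapsed time to age at first vaccination.

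**The concern.** The overall VE of this sensitivity analysis has two descriptions. One applies enrolment-age rates band by band and sums. The other, on its plain reading, applies a single rate from placebo subjects aged 55 or older at vaccination. Apart from removing the youngest band, that second rule ages nobody: a subject vaccinated at 70 receives an average over all placebo subjects from 55 upward. Two programmers could follow the SAP and report different results.

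By stratum, a subject vaccinated at 79.8 who enrols 5.4 years later is 85.2 at enrolment. That subject's expected control cases go to the 80-or-older stratum, while any observed herpes zoster (HZ) counts in 70-79. Observed and expected cases then come from partly different people. SAP 7.3.6 also gives no sums for the 60-or-older and 70-or-older strata that SAP Table 1 requires.

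What is at stake is the credibility of the SAP's check on ageing, not the primary estimate.

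**Working it through.** **1. The SAP's own intervals (SAP 6.3.3 example, dose 2 to first visit).** 1 Nov 2011 to 2 Feb 2016 is 1554 days, and (1554+1)/365 = 4.260. To 5 Jul 2016 is 1708 days, and 1709/365 = 4.682. Both printed figures are reproduced, with divisor 365; the stated 365.25 gives 4.257 and 4.679. The strata use first vaccination, so add the 49-83 days between doses (SAP 5.3), 0.13-0.23 year. The intervals become about 4.4-4.5 and 4.8-4.9 years.

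**2. When the mapping is exact.** With a common interval L and ages uniform within a decade, the share credited to the wrong stratum is |L-5|/10. It is 0 at L = 5.0 and 5.7% at L = 4.43.

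Case-count example at L = 4.43, using Protocol 11.4's 3672 + 2734 expected returners. Assume the 3672 split in thirds by decade, giving 1224 in 60-69 and 1224 + 2734 = 3958 aged 70 or older. Assume 20% of the latter are 80 or older, leaving 3166 in 70-79 and 792 in 80+.
- 60-69 receives 0.943 x 1224 + 0.057 x 3166 = 1335, ratio 1.09.
- 80+ receives 0.943 x 792, about 746, ratio 0.94.

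**3. Varying intervals.** The documents give no age mix or interval distribution, so these are assumed. Simulation: 2 million subjects per scenario; mixes for 50-59/60-69/70-79/80+ of 26/16/46/12, 35/25/32/8 and 20/20/45/15%; four within-stratum age shapes from uniform to declining to zero; rates equal, stepping from 5 to 10 per 1000 at age 60 (Protocol 1.1), or rising 2% per year.

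| Interval (years) | Wrong stratum | Count ratio 50-59 | 60-69 | 70-79 | 80+ |
|---|---|---|---|---|---|
| 5.0 | 0% | 1.000 | 1.000 | 1.000 | 1.000 |
| 4.4-5.6 | 2.1-2.8% | 0.992-1.045 | 1.009-1.066 | 0.979-0.991 | 0.955-1.047 |
| 4.6-5.8 | 1.1-3.0% | 0.970-1.018 | 1.004-1.030 | 0.974-0.995 | 0.982-1.100 |

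If mapped counts are set against the stratum's own follow-up, a true VE of 80% reads 1 - 0.2/ratio: from 1 - 0.2/0.955 = 79.1% to 1 - 0.2/1.100 = 81.8%. If the bands' follow-up travels with their cases, the control-rate ratios are only 0.993-1.017, and within about 0.5% of 1 in 80+. VE then reads 79.9-80.3%.

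**4. Overall rule, by hand, with an exact 5-year shift.** Same split; placebo arm assumed the same size and split as the vaccine arm (7344 and 6075, Protocol 11.4); rates 5 per 1000 below 60 and 10 from 60.
- Summed over enrolment bands: (612 x 5 + 5794 x 10)/6406 = 9.522 per 1000.
- Pooled 55-or-older placebo: (1224 x 5 + 10,971 x 10)/12,195 = 9.498.
- Ratio 0.9975; a summed VE of 80% reads 1 - 0.2/0.9975 = 79.95%.

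So the two rules differ even when the interval is exactly 5 years.

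**5. Overall rule, simulated (4.4-5.6 years), pooled over summed.** Step rates: 0.980-1.028 for three age shapes, VE 79.6-80.5%; maximum 1.083 with ages declining to zero, VE 81.5%. Incidence rising 1% to 3% per year: 0.996 down to 0.907, VE 79.9% down to 77.9%.

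**6. Year 12.** SAP 7.3.3 provides that, when the last year is thin, "data from both year 11 and year 12 will be pooled in the VE analysis", and Table 1 says "yearly follow-up will be computed from one month post dose 2 in the ZOSTER-006/022 studies". One month after dose 2 is 79-113 days after dose 1, 0.216-0.309 year. The latest in-window Year 6 visit is day 2220, 6.078 years (Protocol Table 8). Reaching 11.0 years by then needs an interval above 11 + 0.216 - 6.078 = 5.14 to 11 + 0.309 - 6.078 = 5.23 years.

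**The case against.** **The mapping may be exact by intention.** SAP 7.3.3 speaks of approximate age, the table is offered as an illustration, the 50-54 enrolment row is marked not applicable, and SAP 7.3.6 states that everyone was at least 55 at enrolment. All of this fits a convention of vaccination age plus 5, under which the mapping is exact. But no such convention is stated, SAP 7.2 derives enrolment age differently, and all but one of the ZOSTER-049 row labels refer to age at enrolment. One sentence could settle it.

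**The overall text may not mean one pooled rate.** The incidence rates are in the plural, and step 3 itself uses total subject-years for age-specific follow-up. Dropping placebo subjects aged 50-54 could simply be non-use of the first band's rate. This makes the passage ambiguous rather than plainly wrong, but nothing in it mentions a sum over age bands. The two sections still need reconciling.

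**The stratum denominator is open.** SAP 7.3.3 pairs age-specific control cases with age-specific follow-up, which supports the smaller rate-based error. This stands, and it limits the size.

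**The interval evidence is indirect.** The year-12 provision is conditional, and Protocol Table 8 keeps subjects seen outside the window. A 5.0-year cohort ending at 10.77-10.86 years on day 2220 needs only about 50-84 further days to enter year 12. The worked dates belong to the persistence analysis. Both are supporting evidence, not proof.

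**Inputs.** The 35/25/32/8 mix puts 40% at 70 or older, below the 2734/6406 = 42.7% that Protocol 11.4 implies as a minimum. Dropping that mix changes little.

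**Conclusion.** Both defects stand in the text, and both are confined to a descriptive sensitivity analysis. The clearer one is the overall rule: read as a pooled rate, it does not apply enrolment-age rates. It can move an overall VE of 80% to about 78-80% with incidence rising 1-3% per year, or about 79.6-80.5% under the protocol's rates for most age shapes (81.5% at the extreme). The stratum shift is wrong in principle unless every interval is 5.0 years. On the assumed intervals its effect is -5% to +10% in control counts, largest in 80+, or -1% to +2% in control rates. All sizes rest on the assumed age mixes, age shapes, intervals and gradients.

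A reader might infer three stronger things:
- That the long-term VE itself is biased. It is not affected: the primary analysis uses age at first vaccination and neither rule.
- That the 80+ result is seriously distorted. That needs the stratum's own follow-up as denominator, which the SAP does not state; on the other reading it moves by about 0.5% or less. Sampling error there is larger anyway: if 8-15% of 6406 subjects are 80+ and are followed 6 years at 10 per 1000, 31-58 control cases are expected, or 6-12 vaccine cases at VE 80%.
- That intervals are shown to lie well away from 5 years. The documents show that they vary, not how far.

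Low priority, but worth correcting because two defensible programs could give different answers.

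**What to change.** Rewrite SAP 7.3.6 at subject level:
- Keep each subject in their own vaccination-age stratum.
- Compute expected control cases per subject as ZOSTER-049 person-time times the placebo rate for the actual enrolment-age band (age derived as in SAP 7.2) and region.
- Sum within each stratum, including 60+ and 70+, with that stratum's own follow-up as denominator, and over all subjects for the overall VE. This replaces both the n1+n2 mapping and the pooled 55-or-older rule, and brings SAP 7.3.6 into line with SAP 7.3.3.
- Use the 50-54 placebo rate (IR1) for anyone enrolled below 55.
- Correct the 80-84 row label in the ZOSTER-049 column, which refers to primary vaccination instead of enrolment.
- Show the interval descriptives by stratum already planned in SAP 6.1.1 beside the result.

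Assignment is then correct at any interval by construction, although age stays fixed at enrolment, as it does in the current plan. The data are already held. The cost is one rewritten section and moderate reprogramming. Some age-by-region cells will be sparse and may need collapsing or smoothing, by a rule stated in advance.

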## 7.4. Immunogenicity

For the analysis of immunogenicity, missing or non-evaluable measurements will not be replaced. Therefore, a subject will be excluded from an analysis if all measurements are missing or non-evaluable.

### 7.4.1. Humoral immune response

A seronegative subject is a subject whose Ab concentration is below the cut-off value.

A seropositive subject is a subject whose Ab concentration is greater than or equal to the cut-off value.

The seropositivity rate is defined as the percentage of seropositive subjects.

The Vaccine Response Rate (VRR) for anti-gE is defined as the percentage of subjects who have at least:

- a 4-fold increase in the anti-gE Ab concentration as compared to the pre-vaccination anti-gE Ab concentration, for subjects who are seropositive at baseline, or,
- a 4-fold increase in the anti-gE Ab concentration as compared to the anti-gE Ab cut-off value for seropositivity, for subjects who are seronegative at baseline.

The GMC calculations are performed by taking the anti-log of the mean of the log concentration transformations. Ab concentrations below the cut-off of the assay will be given an arbitrary value equal to half the cut-off for the purpose of GMC calculation.

The Mean Geometric Increase (MGI) is defined as the geometric mean of the within subject ratios of two different timepoints.

- The assay cut-off is the value under which there is no quantifiable result available. For an assay with a specific 'cut\_off', numerical immuno result is derived from a character field (rawres):
  - If rawres is 'NEG' or '-' or '(-)', numeric result= cutt\_off/2,
  - if rawres is 'POS' or '+' or '(+)', numeric result = cut\_off,
  - if rawres is '< value' and value<=cut\_off, numeric result =cut\_off/2,
  - if rawres is '< value' and value>cut\_off, numeric result =value,
  - if rawres is '> value' and value<cut\_off, numeric result =cut\_off/2,
  - if rawres is '> value' and value>=cut\_off, numeric result =value,

- if rawres is ‘<= value’ or ‘>= value’ and value<cut\_off, numeric result =cut\_off/2,
- if rawres is ‘<= value’ or ‘>= value’ and value>=cut\_off, numeric result =value,
- if rawres is a value < cut\_off, numeric result = cut\_off/2,
- if rawres is a value >= cut\_off, numeric result = rawres,
- if rawres is a value >= cut\_off, numeric result = rawres,
- else numeric result is left blank.

- All CI computed will be two-sided 95% CI.

#### 7.4.2. CMI response

- For the descriptive analyses, the frequency of CD4[2+] T-cells upon in vitro stimulation with the gE-antigen (induction condition) is calculated by dividing the number of activated CD4[2+] T-cells (numerator) over the total number of CD4 T-cells involved (denominator). The same calculation will be performed for the frequency computation for any kinds of cells and for each individual activation marker as appropriate.

$$Freq_{Induction}^{CD4[2+]} = \frac{n_{Induction}^{2+}}{N_{Induction}^{CD4}}$$

$n_{Induction}^{2+}$  = number of CD4 T – cells secreting at least 2 activation markers after induction with the antigen

$N^{CD4}$  = Total number of CD4 T – cells involved in the assay (induction )

- The frequency of gE-specific CD4 T-cells for each individual subject is calculated as the difference between the frequency of CD4[2+] T-cells, upon in vitro stimulation with the gE antigen (induction condition) minus the frequency of CD4[2+] T-cells upon in vitro stimulation in medium only (background condition). The differences less or equal to one are imputed to one gE-specific CD4[2+] T-cell per  $10^6$  CD4+ T-cells. The same calculation will be performed for the frequency computation for any kind of cells and for each individual activation marker as appropriate.

$$Freq_{Specific}^{CD4[2+]} = \frac{n_{Induction}^{2+}}{N_{Induction}^{CD4}} - \frac{n_{Background}^{2+}}{N_{Background}^{CD4}} \quad \text{if } \frac{n_{Induction}^{2+}}{N_{Induction}^{CD4}} > 1 + \frac{n_{Background}^{2+}}{N_{Background}^{CD4}}$$

$$Freq_{Specific}^{CD4[2+]} = 1 \quad \text{if } \frac{n_{Induction}^{2+}}{N_{Induction}^{CD4}} \leq 1 + \frac{n_{Background}^{2+}}{N_{Background}^{CD4}}$$

$n_{Induction}^{2+}$  = number of CD4 T – cells secreting at least 2 activation markers after induction with the gE - antigen

$n_{Background}^{2+}$  = number of CD4 T – cells secreting at least 2 activation markers in the medium conditions

$N^{CD4}$  = Total number of CD4 T – cells involved in the assay (induction of background )

- The GM frequency calculations are performed by taking the anti-log of the mean of the log frequency transformations.
- The CMI vaccine response to gE will be based on the gE-specific data. The VRR is defined as the percentage of subjects who have at least:

- a 2-fold increase as compared to the threshold 320 polypositive CD4+ T cells/10E6 CD4+ T cells, for subjects with pre-vaccination T-cell frequencies below the threshold 320 polypositive CD4+ T cells/10E6 CD4+ T cells;
- a 2-fold increase as compared to pre-vaccination T-cell frequencies, for subjects with pre-vaccination above the threshold 320 polypositive CD4+ T cells/10E6 CD4+ T cells.

